#### ECGs

The AE reporting period for a subject enrolled in the study will begin when the subject signs the ICF and continues through the 28-day Follow-up Visit, i.e., 28 days after the last dose of belumosudil.

#### 7 SAFETY

#### 7.1 Safety Parameters

The Common Terminology Criteria for Adverse Events version 4.03 (CTCAE v4.03) will be used for classifying laboratory results and grading AEs. Subjects will be monitored throughout the treatment and follow-up period for occurrence of AEs (acute, delayed, and/or cumulative) as well as for changes in clinical status, vital sign measurements, and laboratory data. Safety parameters to be measured/assessed include vital sign measurements; PE; hematology and serum chemistry results; and ECG recordings.

#### 7.2 Adverse Event Definition

An AE is defined as any untoward medical occurrence in a clinical trial subject associated with the use of a drug, whether or not considered drug-related. An AE can be an unfavorable and unintended sign (e.g., an abnormal laboratory value finding), a symptom, or a disease temporally associated with the use of a drug, without judgment as to causality. An AE can arise from use of the drug (e.g., use in combination with another drug) and from any route of administration, formulation or dose, including an overdose. An AE also includes, but is not limited to, any clinically significant worsening of a pre-existing condition. Examples include:

- Any sign, symptom, physical finding, or laboratory result that has worsened in nature, severity or frequency compared to Baseline
- Reactions from an investigational product including those occurring as a result of an overdose, abuse of the study drug, withdrawal phenomena, sensitivity or toxicity
- Concurrent illness that was not present or worsens in nature, severity, or frequency compared to Baseline
- Injury or accident and/or
- Exacerbation of a pre-existing condition

For the purpose of data collection, all untoward events that occur after informed consent through the 28-day Follow-up Visit are to be recorded on eCRFs by the investigational site.

# 7.3 Evaluating Adverse Events

The Investigator will determine the seriousness, intensity, and causality of AEs based on the definitions that follow.

#### 7.3.1 Serious Adverse Events

### The Sponsor or designee must be notified within 24 hours.

The SAE definition and reporting requirements will be in accordance with Title 21 Part Code of Federal Regulations (CFR) 312.32 and the Guidance for Industry and Investigators Safety Reporting Requirements for Investigational New Drug (INDs) and Bioavailability/Bioequivalence Studies (BA/BE).

SAE: An adverse event is considered "serious" if, in the view of either the Investigator or Sponsor, it results in any of the following outcomes:

- Death: This includes any death that occurs while the subject is "on study" as well as any death that occurs within 28 days after study drug discontinuation. Note: Death is an outcome of an AE, not an AE in itself. The event(s) that caused death (e.g., illness, accident) is the SAE. Death due to any other cause(s) must also be reported as an outcome of the reportable SAE.
- Life-threatening AE: An AE or suspected adverse reaction is considered
   "life-threatening" if, in the view of either the Investigator or Sponsor, its occurrence
   places the subject at immediate risk of death. It does not include an AE or suspected
   adverse reaction that, had it occurred in a more severe form, might have caused death.
- Inpatient hospitalization or prolongation of existing hospitalization: The Investigator should not report hospitalization or prolongation of hospitalization in the following situations: (1) hospitalization or prolongation of hospitalization is needed for a procedure required by the protocol; (2) hospitalization or prolongation of hospitalization is part of routine procedure followed by study center; or (3) hospitalization for survey visits or annual physicals. Note: a hospitalization planned before the start of the study for a pre-existing condition which has not worsened does not count as an SAE.
- Persistent or significant incapacity or substantial disruption of the ability to conduct normal life functions
- Congenital anomaly/birth defect
- Important medical event: An event that may not result in death, be life-threatening, or
  require hospitalization may be considered serious when, based upon appropriate medical
  judgment, it may jeopardize the subject and may require medical or surgical intervention
  to prevent one of the outcomes listed in this definition.

#### 7.3.2 Protocol-Related Adverse Events

Adverse events that are not study drug related may nevertheless be considered by the Investigator or the medical monitor to be related to the conduct of the clinical study, i.e., the event may be related to the fact that a subject is participating in the study. For example, a protocol-related AE may be an event that occurs during a washout period or that is related to a procedure required by the protocol.

### 7.3.3 Relationship to Study Drug

The Investigator will attempt to assess the relationship of the event to study drug using a 5-point scale (not related, unlikely-related, possibly related, probably related, or definitely related; (Appendix G: Determining Relationship of AEs to Study Drug).

### 7.3.4 Recording Adverse Events

All AEs and SAEs are to be accurately recorded on the Adverse Event page of the subject's eCRF during the subject's participation in the study. The severity of each AE will be graded using the CTCAE v4.03 scale. The date of onset as well as the end date of the event also should be recorded or the event should be entered as "ongoing". In addition, the method used to treat the AE and the outcome of the AE also will be noted. In the event that the grade of an AE worsens, an end date should be entered to the initial AE and a new AE entered with the updated grade and date of onset. The Investigator will assess the relationship of the event to study drug.

Note: All SAEs also are to be entered onto an SAE form and sent to the Sponsor or designee within 24 hours.

#### 7.3.5 Serious Adverse Event Reporting

### 7.3.5.1 Timeframe for Reporting

Any death, SAE, or pregnancy (including pregnancy of a partner) experienced by a subject while receiving or within 28 days of receiving study drug, regardless of relationship to study drug, including follow-up information, or any SAE that occurs more than 28 days after receiving study drug, and is believed to be study drug-related, must be promptly reported (within 24 hours of the Investigator becoming aware of the event) by e-mail to the Sponsor (or designee).

SAE Form or Pregnancy Form (initial report or follow-up report) must be sent within 24 hours of becoming aware to: [contact].

Additionally, the Investigator will be able to contact the medical monitor at all times. Refer to sponsor and CRO contact list for up to date contact information.

### 7.3.5.2 SAE Information to be Provided by the Investigator

The SAEs for all enrolled subjects must be recorded on the SAE form (during study participation). This requirement includes all SAEs that occur after informed consent and through the 28-day Follow-up Visit at 28 days after last dose of study drug. In addition, any SAEs that are assessed as at least possibly related to study drug by the Investigator, even if the SAE occurs more than 28 days after the last dose of study drug, must be reported to the Kadmon Pharmacovigilance (or designee) as described below:

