#### 6.2.2 Baseline Visit

Subjects will be evaluated to determine if they meet all inclusion/exclusion criteria. Those signing the ICF will be enrolled in the study.

Note: If the subject was in LTFU in Study KD025-208 or in Study KD025-213, the subject will only have LTFU assessments performed once approximately every 3 months (Section 6.2.5).

Belumosudil will be administered as follows:

- Subject receives same dose of belumosudil as assigned in Study KD025-208 or in Study KD025-213, as appropriate. The first dose may be taken at home or in the clinic.
- Dispense a study drug diary to the subject

The following data will need to be captured from Study KD025-208 or Study KD025-213:

- The dosing group to which the subject was assigned or randomized
- Clinician-reported Global cGVHD Activity Assessment from Day 1
- Any ongoing AEs

The following efficacy assessments will be performed:

Clinician-reported Global cGVHD Activity Assessment

- Response assessment. (Note: all responses will be assessed with respect to Cycle 1 Day 1 of Study KD025-208 or Study KD025-213.)
- PFT (for subjects with lung cGVHD or when lung cGVHD is suspected)
- LSS
- Use of corticosteroid dosage
- Use of other cGVHD therapies

The following safety assessments will be performed:

- Symptom-directed PE
- Vital signs
- Weight and height
- KPS
- Hematology lab testing
- Clinical chemistry lab testing
- 12-lead ECG
- Urine pregnancy test (any positive results will be confirmed with serum testing)
- Use of concomitant medications
- AEs

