### 6.2.5 Long-term Follow-up

Long-term Follow-up will start at Baseline for enrolled subjects who have been permanently discontinued from belumosudil in Study KD025-208 or in Study KD025-213 where they have not yet had an FFS event. The LTFU will occur after the 28-day Follow-up Visit has been completed for enrolled subjects who were actively dosed with belumosudil at Baseline.

Subjects will have LTFU approximately every 3 months until an FFS event occurs. This LTFU assessment will occur by subjects being contacted by telephone, e-mail, or postal mail to confirm survival status, any initiation of new systemic cGVHD therapies, and relapse of underlying disease. Alternatively, this information may be obtained from the subject's medical records.

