# 7.4.2 Follow-Up of Adverse Events

All SAEs and TEAEs (including clinically significant abnormal laboratory values that meet these criteria) will be followed until either resolution of the event or determination by the Investigator that the event has become stable or irreversible. The status of all other continuing AEs will be documented as of 28 days after last dose of study drug.

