### 9.9 Safety Analyses

Safety analyses will be performed on all subjects who receive at least one dose of belumosudil.

Adverse events will be coded using the Medical Dictionary of Regulatory Activities (MedDRA) (Version 24.0 or greater). The number and percentages of subjects experiencing TEAEs will be tabulated by System Organ Class and Preferred Term (PT). The number of events by PT will also be summarized. Tabulation by maximum severity and relationship to treatment will also be included by treatment group.

Summary subject listing will be provided for SAEs, AEs resulting in study discontinuation, and deaths.

Adverse events, SAEs, related AEs, related SAEs, Grade  $\geq$  3 AEs, related Grade  $\geq$  3 AEs, and AEs leading to withdrawal and treatment discontinuation, and deaths will be summarized.

Laboratory results will be summarized by treatment group, incidence of laboratory abnormalities, and worst on-study grade during the treatment period will be summarized. The incidence of Grade  $\geq$  3 laboratory abnormalities under treatment and shifts in toxicity grading from Baseline to highest grade post-baseline will be displayed.

Vital sign measurements and ECGs will be summarized by treatment group at each scheduled time point using descriptive statistics and included in data listings.

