3.8.1 Adverse Events

AEs will be coded using the MedDRA dictionary (Version 24.1 or higher). Treatment-emergent AEs (TEAEs) are any AEs occurring or worsening in severity after the first administration of study medication until 28 days after EOT. All AEs will undergo 4 sets of ratings by Investigator as follows:

- Serious vs. non-serious [based on seriousness criteria of death, life threatening, hospitalization – initial or prolonged, IME, disability or permanent damage, congenital anomaly or birth defects, and required intervention]
- Grades using the 5-point Common Terminology Criteria for Adverse Events (CTCAE 4.03) scale (mild, moderate, severe, life-threatening, or death)
- Causality assessment with respect to study drug classified as either: related (definitely related, related, probably related, and possibly related) or not related (unlikely related, not related).
- The relationship of AEs to cGVHD or the underlying disease

Kadmon Corporation

Page 20 of 26

The number (N) and percentage (%) of patients who experienced at least one TEAE will be summarized by dose group, including tabulation by:

- System Organ Class (SOC) and PT within each SOC in decreasing total frequency
- · Decreasing frequency of PT
- Maximum severity
- Relationship to study drug

These analyses will be repeated for serious TEAEs, events leading to dose modification, events leading to study drug discontinuation, events related to study drug and events related to cGVHD or the underlying disease.

Subject listings will be provided for AEs, SAEs, AEs resulting in study drug discontinuation and deaths. Time to onset and duration of AEs will be included in listings, along with action taken and outcome.

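### Related SAEs more than 28 days after the last dose must be reported, but long-term follow-up does not ask about them, their eCRF entry is unclear, and no SAP table summarises them

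*Protocol*

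**What the plan says.** **Reporting.** Protocol 7.3.5.1 states that "any SAE that occurs more than 28 days after receiving study drug, and is believed to be study drug-related, must be promptly reported", with a 24-hour clock that starts when the investigator becomes aware. Protocol 7.3.5.2 repeats the duty for SAEs rated at least possibly related, "even if the SAE occurs more than 28 days after the last dose of study drug, must be reported to the Kadmon Pharmacovigilance". Neither section sets an end date.

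**Follow-up.** Under Protocol 6.2.5 the LTFU contact, about every 3 months until a failure-free survival (FFS) event, is made "to confirm survival status, any initiation of new systemic cGVHD therapies, and relapse of underlying disease". The same information may instead be taken from medical records. The note to Table 7 lists the same three items. For a subject already in LTFU in the parent study, Protocol 6.2.2 says that "the subject will only have LTFU assessments performed once approximately every 3 months". Protocol 7.1 says in general terms that adverse events, delayed ones included, are monitored through treatment and follow-up.

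**Recording.** Protocol 7.2 says that "all untoward events that occur after informed consent through the 28-day Follow-up Visit are to be recorded on eCRFs". Table 7 runs AE collection from consent to 28 days after the last dose. Protocol 7.3.4 puts all AEs and SAEs on the eCRF AE page for as long as the subject participates in the study.

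**Analysis.** SAP 3.8.1 defines TEAEs as "any AEs occurring or worsening in severity after the first administration of study medication until 28 days after EOT". It tabulates subjects with at least one TEAE and repeats those tabulations for serious, related and other subsets. Its listings of AEs, SAEs and deaths carry no TEAE restriction. Protocol 9.9 promises summaries of "Adverse events, SAEs, related AEs, related SAEs" and further categories, and that sentence does not mention the TEAE window.

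**The concern.** The stated objective (Protocol 2, SAP 2.1.1) is long-term safety and efficacy. A serious event that appears well after dosing stops, and that an investigator attributes to belumosudil, is one of the things such a study is placed to detect. The protocol recognises this by making such events reportable without a time limit. The rest of the plan does not carry the duty through: no scheduled procedure looks for the event, sites have conflicting directions on whether to enter it in the clinical database, and no planned table counts it. The study report could then show related-SAE incidence by treatment group without counting late related events, even where the sponsor's safety department had received them.

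**Working it through.** The plan states no figure for this point, so the check follows one hypothetical event through the documents: a non-fatal SAE, rated possibly related, with onset 60 days after the last dose.

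1. **Is it reportable?** Yes, under Protocol 7.3.5.1 and 7.3.5.2, once the investigator knows of it.

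2. **Does a scheduled procedure bring it to the investigator's attention?** No. The 28-day visit is over: its window ends at day 28 + 7 = 35. The next scheduled step is the LTFU contact or record review, whose three items do not include SAEs. Protocol 7.1 states an intention to monitor delayed events, but neither 6.2.5 nor Table 7 gives a procedure for it after the 28-day visit. The investigator may still learn of the event through routine care, an unscheduled visit (6.2.6) or a record review done for another purpose. That is passive ascertainment.

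3. **Does it go on the eCRF?** The sections point in different directions.
   - Protocol 7.3.4: all AEs and SAEs during participation. The synopsis row on duration of participation describes LTFU, which suggests yes.
   - Protocol 7.2: events through the 28-day visit. Table 7: until 28 days after the last dose. Both suggest that collection has ended.
   - Protocol 7.3.5.2 requires the report to pharmacovigilance but does not say whether the event also goes on the eCRF AE page.

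4. **Does it reach a table?** The TEAE window closes 28 days after end of treatment (taken here as the last dose), and 60 > 28. The SAP's tabulations count subjects with a TEAE, and the serious and related versions repeat them. On the natural reading the event is in none of them.

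5. **Does it reach a listing?** Possibly. The SAE listing is not limited to TEAEs, but the event appears only if step 3 put it in the clinical database. A listing gives no incidence by treatment group.

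The windows also differ slightly at the edge. An SAE on days 29 to 35 can be recorded under 7.2 when the 28-day visit is late, yet it falls outside the TEAE tables.

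**Subjects who enter in LTFU.** They have only LTFU assessments. If the last parent-study dose was more than 28 days before consent, Table 7's AE window (consent to 28 days after the last dose) closes before it opens. For events arising in this study, the late-reporting duty is then the only explicit reporting route, and no scheduled question supports it. SAP 3.2 nevertheless places all enrolled subjects in the analysis set for safety.

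**The case against.** The strongest reply is that expedited reporting and a TEAE window serve different purposes. The first is a pharmacovigilance duty; the second defines on-treatment incidence. Ending both the AE reporting period and the TEAE window at about day 28 is coherent, and Protocol 9.9 can be read with that period in mind. This stands to the extent that the TEAE tables should keep their definition. Adding passively found post-treatment events to them would mix two methods of ascertainment, while SAP 3.6 counts exposure over treatment days only. It does not explain why a category of event that the protocol singles out as reportable has no planned summary.

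Three stronger readings are tempting, and the documents do not support them.

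- A reader might infer that delayed toxicity will be missed. Late related SAEs remain reportable on awareness, 7.3.4 offers a route to the eCRF, the SAP listings can show them, and late deaths enter overall survival while the subject is followed.
- A reader might infer that outcomes of open events cannot be collected, because 7.4.2 requires that "All SAEs and TEAEs (including clinically significant abnormal laboratory values that meet these criteria) will be followed until either resolution of the event" and LTFU has no such item. Outcomes have a place on the eCRF AE page (7.3.4) and on the SAE form with its follow-up reports (7.3.5.2), and unscheduled visits are available.
- A reader might take LTFU to be open-ended. It stops at an FFS event.

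It is also fair to say that 7.2 does not forbid later eCRF entries. The fault there is an unresolved conflict with 7.3.4 and Table 7, not a prohibition.

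**Conclusion.** The point holds in a limited form. Ascertainment of related SAEs after day 28 is passive, the direction on eCRF entry is inconsistent, and no SAP table summarises these events. In a long-term safety study this should be corrected. It does not threaten a hypothesis test or a stopping decision, since the protocol has neither (sections 8 and 9.1).

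No numerical size can be given. The documents state neither how many subjects will enter in LTFU nor how often late related SAEs occur. A reader might take the off-drug share at the parent-study cut-off of 19 February 2020 as a guide: (37 − 7) + (119 − 70) = 30 + 49 = 79 of 37 + 119 = 156 subjects still participating. That does not measure the group affected here. It counts subjects followed for survival who may already have had an FFS event, and such subjects cannot enter under the LTFU criterion (4.3).

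The conclusion assumes that end of treatment in the SAP means the last dose, and that the repeated tabulations in SAP 3.8.1 keep the TEAE restriction throughout, as their wording indicates.

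**What to change.** 1. **Protocol 6.2.5 and the Table 7 note:** add to the existing LTFU contact or record review one item on any SAE considered at least possibly related to belumosudil.
2. **Protocol 7.2, 7.3.4 and Table 7:** reconcile these so that a related SAE with onset after day 28 is entered on the eCRF AE page as well as on the SAE form.
3. **SAP 3.8.1:** add a separate summary of related SAEs with onset more than 28 days after the last dose, giving the number and percentage of subjects by treatment group with the denominator stated. Leave the TEAE tables as they are.

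The cost is a small protocol amendment, with ethics committee submission under Protocol 13, plus one eCRF rule and one additional table. No visit is added. Reported related-SAE counts may rise slightly. Two limits remain: where LTFU is done by record review, the item can be answered only from what the records contain, and it covers subjects only until their FFS event.

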#### Report SAEs on an SAE form within 24 hours of becoming aware to:

[contact].

### Additionally, the Investigator will be able to contact the medical monitor at all times at:

#### A. [contact].

The minimum information required for SAE reporting includes identity of Investigator, site number, subject number, an event description, SAE term(s), onset date, reason why the event is considered to be serious (i.e., the seriousness criteria), and the Investigator's assessment of the relationship of the event to study drug. Additional SAE information including medications or other therapeutic measures used to treat the event, action taken with the study drug due to the event, and the outcome/resolution of the event will be recorded on the SAE form. Forms for reporting SAE will be provided to the study sites.

When reporting SAE, the following additional points should be noted:

- When the diagnosis of an SAE is known or suspected, the Investigator should report the
  diagnosis or syndrome as the primary SAE term, rather than as signs or symptoms. Signs
  and symptoms may then be described in the event description. For example, dyspnea
  should not be used as an SAE term if the diagnosis which caused the dyspnea is known to
  be malignant pleural effusion.
- Death should not be reported as an SAE but as an outcome of a specific SAE, unless the
  event preceding the death is unknown. In the exceptional case where the events leading

to death are unknown, then death may be used as an event term. If an autopsy was performed, the autopsy report should be provided.

While most hospitalizations necessitate reporting an SAE, some hospitalizations do not require SAE reporting: (1) elective or previously scheduled surgery (e.g., a previously scheduled ventral hernia repair); (2) procedures for pre-existing conditions that have not worsened after initiation of treatment; (3) pre-specified study hospitalizations for observation; and (4) events that result in emergency room stays of less than 24 hours and that do not require admission.

However, SAEs must be reported for any surgical or procedural complication resulting in prolongation of the hospitalization.

In all cases, the Investigator should continue to monitor the clinical situation and report all material facts relating to the progression or outcome of the SAE as a follow-up in the same timeframe and manner as the initial SAE report. Furthermore, the Investigator may be required to provide supplementary information as requested by the Kadmon Pharmacovigilance or designee.

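### Protocol Sections 7.3.1 and 7.3.5.2 conflict on planned admissions: elective surgery for a condition that arose or worsened on study is an SAE under one and needs no SAE report under the other

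*Protocol*

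**What the plan says.** Protocol Section 7.3.1 makes inpatient hospitalisation, or its prolongation, a ground for seriousness. It then lists three situations that should not be reported. The first is where "hospitalization or prolongation of hospitalization is needed for a procedure required by the protocol"; the others are routine procedures of the centre, and survey visits or annual physicals. A note adds that "a hospitalization planned before the start of the study for a pre-existing condition which has not worsened does not count as an SAE".

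Protocol Section 7.3.5.2, which tells the investigator what to send, gives its own list of four exempt items:

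- The list opens by stating that "some hospitalizations do not require SAE reporting: (1) elective or previously scheduled surgery (e.g., a previously scheduled ventral hernia repair").
- A separate entry, item (2), deals with "procedures for pre-existing conditions that have not worsened after initiation of treatment".
- Item (3) covers observation stays that the study sets in advance.
- The last entry, item (4), concerns "events that result in emergency room stays of less than 24 hours and that do not require admission".

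The section then limits its own list by adding that "SAEs must be reported for any surgical or procedural complication resulting in prolongation of the hospitalization".

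The SAE criteria page at the front of the protocol names inpatient hospitalisation as a seriousness outcome and points to Section 7.3.1. SAP Section 3.8.1 lists hospitalisation, whether a new admission or an extended stay, among the seriousness criteria. Neither exempts elective surgery.

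**The concern.** The study objective is long-term safety and efficacy. SAEs are a named safety endpoint (Protocol Section 6.4), and SAP Section 3.8.1 repeats the TEAE tabulations for serious events. There is no control arm, so the observed SAE proportion is itself the result.

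If the definition and the reporting instruction disagree, two sites can classify the same admission in opposite ways, each following the protocol. The instruction that sites use when deciding whether to complete an SAE form is the more permissive one for elective surgery. The sponsor selects events for expedited reporting from the SAEs (Protocol Section 7.3.5.4), so an event left off the form may not reach that review.

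**Working it through.** The documents give no figure to reproduce. The check is a comparison of the two lists, one test case and one line of arithmetic.

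**Step 1: the lists side by side.**

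| Type of admission | Section 7.3.1 | Section 7.3.5.2 | Conflict? |
|---|---|---|---|
| Required by the study | Exempt | Item (3), study observation | Roughly the same |
| Routine centre procedure | Exempt | Not listed | In one list only |
| Survey visit or annual physical | Exempt | Not listed | In one list only |
| Planned or elective | Exempt only if planned before the study, and pre-existing, and not worsened | Item (1): surgery exempt with none of these conditions | **Yes** |
| Procedure for a pre-existing, unworsened condition | Exempt only if also planned before the study | Item (2): exempt, with worsening judged from the start of treatment | Different anchor |
| Short emergency room stay without admission | Not an inpatient admission | Item (4): exempt | No |

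**Step 2: can item (1) carry the 7.3.1 conditions by implication?** Its wording joins elective and previously scheduled surgery with *or*, so elective surgery qualifies on its own. Item (2) states the requirement of a pre-existing, unworsened condition separately. If item (1) already contained that requirement, item (2) would largely repeat it. The natural reading is that item (1) is not so limited.

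**Step 3: test case.** A subject develops a condition during the study and is admitted for an uncomplicated elective operation.

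- Section 7.3.1: the admission is inpatient. It is neither protocol-required nor an annual visit, and it fails the note because the condition is new and the admission was not planned beforehand. It is an SAE, unless the site treats it as a routine centre procedure.
- SAE criteria page and SAP Section 3.8.1: serious by hospitalisation.
- Section 7.3.5.2 item (1): no SAE report needed.

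If instead the condition existed before but worsened on study, the note in 7.3.1 still fails and item (1) still exempts the operation.

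**Step 4: scale.** Planned enrolment is about 70 (Protocol Section 4.1). One subject whose only SAE is left out changes the subject-level SAE proportion by 1/70 = 0.0143, or about 1.4 percentage points. A subject who has another SAE changes it by nothing.

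**Step 5: anchor dates.** The 7.3.1 note counts from the start of the study; item (2) of 7.3.5.2 counts from the start of treatment. Actively treated subjects began belumosudil in Study KD025-208 or KD025-213, so these dates differ. A condition that arose during the parent study is pre-existing on the first anchor and not on the second.

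**The case against.** The strongest reply is that 7.3.1 is the definition and 7.3.5.2 governs only the SAE form. Under Protocol Section 7.3.4 all AEs and SAEs go on the eCRF adverse event page, and SAP Section 3.8.1 tabulates serious TEAEs from the investigator's rating, with no elective-surgery exemption. On that view the tables could be right even where a form is missing. This stands in part: loss from the tables is possible, not shown, because it requires a site to carry the 7.3.5.2 exemption over into its seriousness rating. Loss of the SAE report follows directly from the text. It can also be said that the only example is a previously scheduled repair, which invites a narrow reading. That is fair, but it does not override the unqualified word *elective*.

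Three stronger readings are tempting, and the documents do not support them:

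- **That item (4) removes life-threatening or important medical events treated in an emergency room.** The lead-in to the list concerns hospitalisations, and no admission occurs in these cases. The other seriousness criteria in 7.3.1 stand separately, and nothing in 7.3.5.2 withdraws them.
- **That 7.3.5.2 always yields fewer SAEs.** Section 7.3.1 exempts routine centre procedures and survey or annual visits, which 7.3.5.2 does not list. The direction holds for the elective-surgery item only.
- **That late-emerging harm disappears from the study.** A new or worsened condition is still an AE (Protocol Section 7.2), is graded and rated for relatedness, and enters the AE and Grade 3 or higher summaries (Protocol Section 9.9). It may be serious on another criterion, and complications that prolong the stay must be reported.

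**Conclusion.** The contradiction on planned admissions is in the text and should be corrected. Item (1) of Section 7.3.5.2 is the outlier against Section 7.3.1, the SAE criteria page and the SAP. What can be lost is the SAE report and possibly the seriousness flag, not the event.

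The size is about 1.4 percentage points per affected subject with no other SAE. This assumes a denominator of about 70; with fewer subjects in the table the step would be larger. The documents give no frequency for such admissions, so a total effect on the SAE proportion cannot be estimated from them. The conclusion also assumes that the operation is not classed as a routine centre procedure and meets no other seriousness criterion. No hypothesis test is affected, since none is planned.

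**What to change.** - Keep one exemption list, in Protocol Section 7.3.1, and have 7.3.5.2 refer to it. Decide explicitly whether the items now found in only one list stay.
- Make the elective-surgery item carry the 7.3.1 conditions: planned beforehand, for a condition that already existed, with no worsening since.
- Choose one anchor date and state it. Anchoring to the start of this study exempts surgery planned during a parent study for an unchanged condition that arose there. Anchoring to the first belumosudil dose would make such an admission an SAE here. Either can be defended, but the choice should be stated.
- State that the exemptions concern the hospitalisation criterion only, so an event that meets any other criterion in 7.3.1 is still an SAE. This also settles any doubt about item (4).
- Align the seriousness criteria in SAP Section 3.8.1 with the final list.

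The cost is a protocol wording change, a clarification to sites and a few more SAE reports.
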